The primary end point of the study will be the non-inferiority in PRU measured at 4 hours of cangrelor plus prasugrel concomitantly administered at the start of PCI versus prasugrel only administered at the start of PCI (group 2 vs. group 1). Non-inferiority will be assessed using a 95% confidence interval (CI) of the difference in mean PRU between the two arms. Under the assumption of 0 difference in mean PRU between group 1 and group 2 and a common standard

deviation of 50 PRU, a sample size of 22 patients per group will allow for the 95% CI to stay within ± 45 PRU with a 90% power and alpha=0.05. Considering a 25% data attrition rate due to GPI use, hemolysis, drop out or technical problems, 28 patients per group will need to be randomized in order to ensure complete available data for analysis. Considering the 3 arms of treatment up to 84 patients will need to be randomized. The sample size of this study was established according to results of previous PD investigations [28,37]. In line with previously reported investigations, 45 PRU was chosen for the noninferiority margin for the upper 95% CI limit of the difference [29,30]. Group 3 will be included in study design as this strategy represents current standard of care for the transition from cangrelor to prasugrel. However, the study will be powered to assess non inferiority of group 2 vs. group 1. Therefore, all other end points will be considered exploratory and will include the comparisons of PD and PK parameters, and P2Y₁₂ gene receptor level expression between all treatment arms at each time points, as well as the comparisons of rates of high on-treatment platelet reactivity (HPR). HPR will be defined as PRU>208 and PRI>50%, in line with consensus definitions [38].

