Conformity to the normal distribution will be evaluated for continuous variables with the Kolmogorov-Smirnov test. For baseline characteristics, continuous variables will be expressed as mean ± SD or median [IQR]. One-way analysis of variance or Kruskal-Wallis test will be used to compare continuous variables. Chi-squared test will be used to compare categorical variables among groups. An analysis of covariance (ANCOVA) method with a general linear model, with treatment as the main effect and baseline values of platelet reactivity as a covariate, will be used to evaluate the primary end point as well as all between-group comparisons at each time point. Least-square mean (LSM) differences in PRU between group 1 and group 2 and the corresponding 2-sided 95% CI for the difference will be obtained to assess non-inferiority based

on the ANCOVA model. Given the exploratory nature of comparisons for secondary end points, correction for multiple comparisons will not be performed. A 2-tailed p value of <0.05 will be considered to indicate a statistically significant difference for all the analyses performed. Statistical analysis will be performed using SPSS version 22.0 software (SPSS Inc., Chicago, Illinois).

The safety population will include all randomized patients exposed to study medication. The PD population will include all patients with PD data and without a major protocol deviation thought to affect significantly the PD and PK of cangrelor or prasugrel. The PD population will be used for analysis of all primary and secondary end points. Erroneously treated patients (eg, those randomized to one treatment but actually given the other) will be accounted for based on the actual treatment received.

Publication Strategy/Additional Information

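### The stated 90% power for the primary non-inferiority test does not match its two-sided 95% CI rule: 22 per arm gives about 83%, or about 66% if the ±45 wording is taken literally

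*Combined protocol and SAP*

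**What the plan says.** All of this stands in the section on study endpoints, sample size calculation and statistical analysis.

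- The primary comparison is group 2 (cangrelor and prasugrel together at the start of PCI) against group 1 (prasugrel alone): "The primary end point of the study will be the non-inferiority in PRU measured at 4 hours".
- The sample size is set "Under the assumption of 0 difference in mean PRU between group 1 and group 2", with a common SD of 50 PRU. It concludes that "a sample size of 22 patients per group will allow for the 95% CI to stay within ± 45 PRU with a 90% power", at an alpha of 0.05 whose sidedness is not given.
- Later in the same paragraph the margin is attached to one limit only: "45 PRU was chosen for the noninferiority margin for the upper 95% CI limit of the difference".
- The analysis text settles the interval: from an ANCOVA adjusted for baseline platelet reactivity, "the corresponding 2-sided 95% CI for the difference will be obtained to assess non-inferiority".
- Attrition is put at 25%, and 28 patients per group are to be randomized. All end points other than this comparison are exploratory.

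**The concern.** Two things do not fit together. First, comparing the upper limit of a two-sided 95% interval with a margin is a one-sided test at 0.025, but 22 per group looks like the answer to a one-sided 0.05 calculation. Second, the paragraph gives two success rules. Keeping the interval within ±45 is an equivalence rule on both limits; testing the upper limit against 45 is a non-inferiority rule. They have different power and can disagree on the same data.

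The aim of the trial is to rule out a drug-drug interaction, and this is the one comparison it is sized for. If the power is overstated, a failed test will be read against a sensitivity that the design does not have.

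**Working it through.** **Inputs, all from the plan:** true difference 0; SD σ = 50; margin Δ = 45; n = 22 evaluable per arm; target power 90%; two-sided 95% CI.

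**Reproducing the plan's figure.** The normal formula is n = 2(z₁₋α + z₁₋β)²(σ/Δ)², with z₁₋β = 1.282.

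- One-sided α = 0.05: 2 × (1.645 + 1.282)² × (50/45)² = 21.1, so **22**. This is the plan's number.
- One-sided α = 0.025: 2 × (1.960 + 1.282)² × (50/45)² = 25.9, so **26**.

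**Power at n = 22, upper-limit rule.** The standard error is 50 × √(2/22) = 15.08, and 45/15.08 = 2.985.

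- Normal, one-sided 0.025: Φ(2.985 − 1.960) = Φ(1.025) = 84.7%.
- Normal, one-sided 0.05: Φ(2.985 − 1.645) = Φ(1.340) = 91.0%.
- Non-central t (42 df, non-centrality 2.985): 83.0% at 0.025 and 90.2% at 0.05.

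**Power at n = 22, both limits within ±45.**

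- Normal, 95% CI: 2 × 0.847 − 1 = 69.5%.
- t-based, 95% CI, by simulation (1,000,000 draws): 66.2%.
- With a 90% CI the same rule gives 80.4% (t) or 82.0% (normal), so the equivalence reading does not produce 90% either.

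| Rule at n = 22 | 95% CI (t) | 90% CI (t) |
|---|---|---|
| Upper limit below 45 | 83.0% | 90.2% |
| Both limits within ±45 | 66.2% | 80.4% |

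Only the upper-limit rule with a 90% CI gives the stated power, and the plan nowhere mentions a 90% CI or a one-sided 0.05 test.

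**Evaluable patients per arm for 90% power with the 95% CI (t-based).** The upper-limit rule needs 27 (90.1%; 26 gives 88.9%). The ±45 rule needs 34 (91.1%; 33 falls just short at just under 90%).

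**Can the two rules disagree?** The expected 95% half-width at n = 22 is about 2.02 × 15.08 = 30 PRU. An observed difference (group 2 minus group 1) of −20 would give about −50 to +10, which passes on the upper limit and fails ±45.

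**The case against.** The strongest reply is that the planned ANCOVA recovers the lost power. If 50 is the unadjusted SD, the residual SD is 50√(1 − r²), where r is the correlation between baseline and 4-hour PRU. Power at 22 per arm is then 84.5% for r = 0.2, 88.9% for r = 0.4 and 90.4% for r = 0.45. Reaching 90% needs a residual SD of about 44.98, so r = √(1 − (44.98/50)²) ≈ 0.44. These correlations are assumptions: the plan states none and uses none in the sample size. If 50 is already the residual SD, nothing is gained. Pooling the error variance over three arms (63 df) moves power only to 83.6%. ANCOVA may help, but it does not support the 90% as written.

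A second reply is that 28 per arm are randomized, and 28 evaluable would give 91.1%. That holds only with no losses. The plan expects 25%, and 28 × 0.75 = 21 evaluable, where power is 81.2%.

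Third, ±45 may be loose wording, since everything else in the section describes non-inferiority. That is fair. The upper-limit rule is the better reading, 83% is the main figure, and 66% applies only to the literal sentence. The rules would typically split only when group 2 has the lower PRU, by more than about 15.

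Finally, the error is conservative. The 95% interval is the stricter choice, so a false claim of non-inferiority becomes no more likely. This also stands: the fault lies in the stated power and the duplicated rule, not in control of the type I error.

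**Conclusion.** The concern holds. With a true difference of 0, SD 50, margin 45, 22 evaluable per arm and no credit for the covariate, the stated two-sided 95% CI gives 83.0% power for the upper-limit rule, 7 points below the claim (5 points by the normal approximation). The risk of a false failure is about 17% instead of 10%. Read literally, the ±45 sentence implies about 66% power and a 34% risk. The figure of 22 is not a slip in the formula; it comes from an alpha that conflicts with the interval the plan commits to.

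**What to change.** Keep one decision rule, the upper limit, and replace the power sentence with wording such as:

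> With 22 evaluable patients per arm, an SD of 50 PRU and a true difference of 0, the upper limit of the two-sided 95% CI for group 2 minus group 1 lies below +45 PRU with about 83% power.

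Delete the phrase about staying within ±45. The margin, analysis model and number randomized do not change. The cost is one sentence and a less favourable stated power.

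The new sentence is conditional on 22 evaluable patients. The plan's own 25% loss from 28 leaves 21, so the text should either give about 81% for that case or reconcile the attrition allowance.

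If the sponsor prefers to keep 90%, the upper-limit rule needs 27 evaluable per arm. At 25% loss that is 27/0.75 = 36 randomized per arm, or 108 over three arms instead of 84. If the sponsor relies on ANCOVA instead, the assumed baseline correlation should be stated and justified.

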The Switching Antiplatelet Therapy-6 (SWAP-6) study will be a prospective, randomized, open label PD and PK study conducted in high-risk patients undergoing PCI. Patients presenting with a non-ST-segment elevation ACS (NSTE-ACS), including unstable angina (UA) and NSTE-myocardial infarction (NSTEMI), or with stable CAD but deemed at high risk undergoing an invasive management strategy as part of their standard of care will be screened. The study will be performed at the Division of Cardiology of University of Florida Health, Jacksonville, Florida. Patients will be screened by Cardiology Research staff, who will verify that all candidates meet inclusion and exclusion criteria, and obtain their written informed consent to participate in the study prior to undergoing their diagnostic invasive evaluation to define coronary anatomy. Results from blood tests performed within the last 90 days will be considered valid for screening purposes. If these are not available, a blood sample will be collected for the screening phase.

After undergoing invasive diagnostic evaluation of coronary anatomy, patients undergoing PCI will be considered eligible for randomization. Using a computer-based randomization system, patients will be randomized in a 1:1:1 fashion to one of the following treatment arms: a) prasugrel only administered at the start of PCI (group 1); b) cangrelor plus prasugrel concomitantly administered at the start of PCI (group 2); c) cangrelor administered at

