Subjects will be identified with a number and data collection sheets will all be stored in a locked area. Data will be kept for 6 years after enrollment ends to comply with HIPAA regulations. Patients will receive a handout with the names and telephone numbers of the doctors involved in the study. Study subjects will be identified first (months 1-17): we expect to randomize 5 subjects monthly and complete enrollment in 17 months (total: 84 subjects randomized). Months 18-20 will be implied for statistical analysis and manuscript preparation. Results will be presented at the first available major cardiovascular meeting (e.g. AHA, ACC, ESC), and final manuscript will be submitted to publication to one of major cardiovascular journals (e.g. JACC, Circulation, European Heart Journal).

Possible Discomforts and Risk

In clinical trials, the most common clinical side effect of cangrelor was bleeding. Severe/moderate bleeding occurred in 0.8% of patients receiving cangrelor, as compared to 0.6% of those receiving placebo. Other side effects include dyspnea (1.3%), worsening renal function (3.2% of patients with severe renal impairment), and hypersensitivity (0.05%) [5]. In clinical trials, the most common clinical side effects of prasugrel were blurred vision, dizziness, headache, nervousness; infrequent events included intracranial hemorrhage (0.79%) and severe neutropenia (< 0.1%). The most important adverse effect associated with the use of prasugrel is bleeding (2.4%) [39]. However, both cangrelor and prasugrel are standard of care therapies and would be potentially utilized as part of standard of care treatment in this study.

All clinical events described above, if they were to occur, as well as death, myocardial infarction, stroke, and urgent revascularization procedure with PCI or coronary artery bypass grafting will be recorded. Bleeding data will be collected using BARC definitions [40]. Clinical events will be evaluated by a local committee, comprised of 2 faculty members (2 cardiologists), not directly involved in the research. In the event of a report of a serious adverse event the local committee will meet and antiplatelet treatment management will be managed according to physician recommendation.

Conflict of Interest

[name] (Sub-Investigator) is a consultant for Chiesi, the maker of cangrelor.

References

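### Randomizing 28 per arm leaves 21 evaluable patients at the plan's own 25% attrition rate, one short of the 22 required; 22 was apparently multiplied by 1.25 rather than divided by 0.75.

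*Combined protocol and SAP*

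**What the plan says.** All the figures are in the section on study endpoints, sample size calculation and statistical analysis. With a true difference of 0, a common SD of 50 PRU, a margin of 45 PRU, 90% power and alpha 0.05, the plan arrives at "a sample size of 22 patients per group". It then makes an allowance for lost data: "Considering a 25% data attrition rate due to GPI use, hemolysis, drop out or technical problems, 28 patients per group will need to be randomized". The stated purpose is that the data available for analysis be complete. The trial total follows: "Considering the 3 arms of treatment up to 84 patients will need to be randomized". The enrolment timeline under Publication Strategy/Additional Information repeats it ("total: 84 subjects randomized"). Allocation is equal across the three arms (Study design: "patients will be randomized in a 1:1:1 fashion").

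No inflation formula is given and no replacement of lost patients is described. The primary analysis uses the PD population, meaning patients with PD data and no major deviation affecting PD or PK.

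**The concern.** An attrition allowance exists so that the evaluable number still meets the target after the assumed loss. The three figures given (22 needed, 25% lost, 28 randomized) cannot all hold together. The listed causes of loss (glycoprotein inhibitor use, hemolysis, drop-out, technical failure) remove usable platelet data from patients already randomized. Because the primary analysis is restricted to the PD population, each such loss comes out of the group 2 versus group 1 comparison, the only one the study is powered for. The total of 84 is worded as an upper limit, so the text offers no room to make up the shortfall. The plan therefore claims a property for its sample size that its own assumptions do not deliver.

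**Working it through.** **Inputs, all from the sample-size and analysis text:** evaluable target 22 per group; attrition 25%; randomized 28 per group, 84 in total; difference 0; SD 50 PRU; margin 45 PRU; power 90%; alpha 0.05 with no side stated in the sample-size sentence; two-sided 95% CI for the non-inferiority test.

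**Reproducing the 22.** For a non-inferiority comparison of means, n per group = 2 × [SD × (z for alpha + z for power) / margin]².
- One-sided 0.05: 2 × [50 × (1.645 + 1.282)/45]² = 21.1, so 22. This matches the plan. The non-central t calculation also gives 22, with power 90.2%.
- One-sided 0.025, which corresponds to the two-sided 95% CI: 25.9, so 26 (27 by non-central t). This does not match.

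**Reproducing the 28.**
- 22 × (1 + 0.25) = 27.5, rounded up to 28. This matches.
- 22 / (1 − 0.25) = 29.33, rounded up to 30. This does not.

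Since no formula is given, the multiplication is an inference, but it gives the stated figure exactly.

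**Checking the 28 against the plan's own rate.**
- Evaluable per arm: 28 × 0.75 = 21, below 22.
- Largest loss that still leaves 22: (28 − 22)/28 = 21.4%.
- 29 per arm: 29 × 0.75 = 21.75, still below 22.
- 30 per arm: 30 × 0.75 = 22.5, which meets the target. Total 3 × 30 = 90, which is 6 more than 84; 4 of these 6 fall in the two arms of the primary comparison.

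**Effect on power** (non-central t, difference 0, SD 50, margin 45, no covariate adjustment):

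| Evaluable per arm | One-sided 0.05 | Two-sided 95% CI (one-sided 0.025) |
|---|---|---|
| 22 | 90.2% | about 83% |
| 21 | 88.9% | 81.2% |

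The attrition step alone costs 1.3 points in the first column and 1.8 in the second.

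**Chance variation in the losses.** Suppose each patient is lost independently with probability 0.25. This is an assumption; the plan gives only a rate. Then the chance that an arm of 28 keeps at least 22 is 0.428, and the chance that both primary arms do is 0.428² = 0.183. With 30 per arm the figures are 0.674 and 0.454.

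**The case against.** Nobody can dispute that 28 × 0.75 is 21. The case on the other side is about size and attribution, and much of it is fair.

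- **The slip is worth one patient per arm.** Its own cost is 1 to 2 points of power. Most of the distance from 90% to 81%, about 7 points (90.2% to 83%), arises because the 22 rests on one-sided 0.05 while the analysis uses a two-sided 95% CI. This stands: the 81% must not be read as the result of the attrition step.
- **The 18% figure looks worse than it is.** Even 30 per arm brings both arms to 22 only 45% of the time, because inflating for expected loss never guarantees a target. This stands. Averaging power over the same random losses gives 88.5% with 28 per arm against 90.4% with 30 at one-sided 0.05, and 80.7% against 83.5% for the two-sided interval, a difference of 2 to 3 points.
- **The ANCOVA may recover some power.** The sample size ignores the baseline covariate. The plan gives no correlation. If it were 0.2 to 0.3 (an assumption), power at 21 per arm would be about 90.0% to 91.3% at one-sided 0.05 and about 82.7% to 84.7% for the two-sided interval. That could offset the missing patient, but the plan does not rely on it and it does not make 28 × 0.75 equal 22.
- **The 25% might be meant as a fraction of the evaluable number.** Then 28 would be consistent, but the implied loss among randomized patients would be at most 21.4%, which is not the natural meaning of a data attrition rate.

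None of this reconciles the three stated figures.

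**Conclusion.** The concern holds. At 25% attrition, 28 randomized per arm gives an expected 21 evaluable, not 22, and the total of 84 inherits the shortfall. The figure consistent with 22 evaluable and 25% loss is 30 per arm, 90 in total. This rests only on the plan's own numbers and on the absence of any replacement rule; it does not depend on how the authors arrived at 28.

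The consequence is modest: one evaluable patient per arm and 1.3 to 1.8 points of power, assuming SD 50 and no true difference. It does not undermine the design. It does add to a larger overstatement of power that comes from the side of the test, and the claim that 28 per arm secures complete data is not correct as written.

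**What to change.** Restate one figure and keep 84 patients. Either of these would do:

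- State that 28 per arm allows for about 21% attrition while retaining 22 evaluable.
- Keep 25% and state that it leaves 21 evaluable per arm, giving about 81% power for the two-sided 95% CI (89% on the one-sided 0.05 basis that produced the 22). Name the basis, so that the drop from 90% is not put down to attrition alone.

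Both cost only an edit, with a slightly less favourable attrition or power statement.

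If the sponsor wants to keep both 25% and 22 evaluable, randomize 30 per arm and change the total to 90 in the sample-size section and the enrolment timeline. At the planned 5 patients a month, the 6 extra patients add 6/5 = 1.2 months. This restores the 22 but not 90% power for the two-sided interval, which would be about 83% at 22 per arm before any gain from the baseline covariate. Whichever route is taken, write the inflation formula, evaluable number divided by one minus the attrition rate, into the text.

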The transition from cangrelor to prasugrel is associated with transient recovery of platelet reactivity, in particular within 1 hour after cangrelor discontinuation, which could be explained by a DDI similar to that described for clopidogrel [9]. However, it was observed that recovery of platelet function was attenuated when prasugrel was administered 30 minutes before stopping the cangrelor infusion [9]. Accordingly, it is recommended that prasugrel be administered at the end of cangrelor infusion or 30 minutes prior to discontinuation of infusion [3,4,9]. However, recently the ExcelsiorLOAD2 (Impact of Extent of Clopidogrel-Induced Platelet Inhibition during Elective Stent Implantation on Clinical Event Rate - Advanced Loading Strategies) study showed that prasugrel 60 mg LD given at the start of a 2-hour infusion of cangrelor was associated with sufficient platelet inhibition post-cangrelor, with only rare cases of high platelet reactivity (HPR) [19]. Moreover, there were no differences with levels of platelet reactivity and HPR rates compared with those observed with ticagrelor, which was also given at the start of the cangrelor infusion. These observations may be attributed to relatively higher concentration and longer half-life of prasugrel's active metabolite compared with that of clopidogrel [20-23]. However, ExcelsiorLOAD2 was not powered to test the non-inferiority on PD effects between prasugrel and ticagrelor, but only for the comparison of prasugrel versus clopidogrel. Moreover, whether similar findings would be observed with longer infusions of cangrelor (e.g., up to 4 hours) is unknown. Therefore, although the PD results of this study provide some support on the safety of administering prasugrel at the start of cangrelor infusion, the trial design does not allow to rule out a DDI given that there was no comparator arm in which prasugrel was either given alone or at the end of cangrelor infusion [24]. Moreover, pharmacokinetic (PK) assessments,

pivotal to help elucidate a DDI, were not performed. Accordingly, recommendations on timing of prasugrel administration in cangrelor treated patients remain unchanged.

STUDY RATIONALE

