the start of PCI plus prasugrel administered at the end of the cangrelor infusion (group 3). Prasugrel will be used in line with FDA recommendations using a 60mg LD followed by a 10mg daily maintenance dose started 24 hours after LD administration [25]. Cangrelor will be used at the FDA recommended dose using a 30 μ g/kg bolus followed by 4 μ g/kg/min infusion [26]. Study drugs will be administered before passing of the guidewire. The duration of cangrelor infusion will be 2 hours or until the end of PCI (whichever is longer). All patients will be on a background of aspirin therapy (325 mg loading dose followed by 81 mg daily maintenance dose). Patients will be managed according to standard of care. The interventional procedure will also be performed according to standard of care with choice of anticoagulant (heparin or bivalirudin) at the discretion of the operator. PK and PD assessments will be conducted at 7 time points: baseline, 30 minutes after administration of randomized treatment, end of PCI (defined as when the guide catheter is removed at procedure completion), 1 hour, 2 hours, 3 hours and 4 hours after administration of randomized treatment. Figure 1 illustrates the overall study design. In patients in which the infusion will be maintained for more than 2 hours (until the end of PCI), the 3-hour and 4-hour after time points will be collected 1 hour and 2 hours after stopping cangrelor, respectively.

Although the study will have an open-label design, laboratory personnel will be blinded to treatment assignments. During hospital stay, major adverse cardiac events (death, myocardial infarction, stroke, and urgent revascularization procedures), serious adverse events (bleeding and other adverse events), as well as non-serious adverse events considered to be study related will be collected. After completing the study, decisions on medical management, including the choice and duration of antiplatelet therapy will be at the discretion of the treating physician.

Figure 1. Overall study design

Study Population

Inclusion criteria:

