3) Total Thrombus-Formation Analysis System (T-TAS): T-TAS is an automated microchip flow chamber system for the quantitative analysis of the thrombus formation process under blood flow conditions. T-TAS allows measurement of thrombus formation using the PL-chip (Diapharma, West Chester Township, OH) [34]. The PL-chip contains 25 capillary channels (width 40 μm, depth 40 μm) coated with type I collagen and is specifically designed for quantitative analysis of platelet thrombus formation, including platelet adhesion and aggregation, granule secretion, and thrombus growth in the absence of coagulation and fibrinolysis systems. In measurements using the PL-chip, a blood sample collected in a hirudin containing blood sampling tube. The platelet aggregates gradually increase in size and, in the process, occlude the capillary, resulting in an increase in flow pressure. In the present study, total platelet-derived thrombogenicity is expressed as the area under the flow pressure curve for the first 10 min for the PL-chip tested at a

flow rate of 18 μ L/min (PL18-AUC10). Low PL18-AUC10 reflect reduced thrombus growth and rapid breakdown of the thrombus.

3) Pharmacokinetic (PK) assay: Determination of prasugrel's active metabolite concentration in plasma will be performed using liquid chromatography with tandem mass spectrometry according to standard protocols as previously described [27,35]. Blood will be drawn into standard EDTA tubes and within 30 seconds a derivatizing agent (3'-methoxyphenacylbromide) will be added to capture and stabilize the active metabolite. The geometric mean area under the concentration-time curve through the sampling time of the last quantifiable prasugrel's active metabolite concentration (AUC[0-t_{last}]) will be calculated and the maximum observed plasma concentration (Cmax) and time to Cmax (Tmax) of Pras-AM will be recorded.

4) $P2Y_{12}$ gene receptor level expression: Gene expression in platelets will be performed using standard protocols. In particular, purified platelets are dissolved in Trizol reagent (Invitrogen) and total RNA will be extracted using RNA minipres kit (Zymos research) according to manufacturer's protocol. P2Y₁₂ mRNA expression will be measured with real-time PCR using SYBR green and specific primers as previously described [36].

Study endpoints, sample size calculation and statistical analysis

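### The all-arm exploratory PK comparisons include group 3, which has only two post-prasugrel samples against six in groups 1 and 2, so its AUC[0-tlast] is expected to be lower even if drug exposure is identical

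*Combined protocol and SAP*

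**What the plan says.** **Dosing and sampling (Study design).** Groups 1 and 2 take the prasugrel load at the start of PCI. Group 3 takes it when the cangrelor infusion ends. On infusion length the section states: "The duration of cangrelor infusion will be 2 hours or until the end of PCI (whichever is longer"). PK and PD samples share seven time points: baseline, 30 minutes, end of PCI, and then "1 hour, 2 hours, 3 hours and 4 hours after administration of randomized treatment". If the infusion runs past 2 hours, "the 3-hour and 4-hour after time points will be collected 1 hour and 2 hours after stopping cangrelor, respectively".

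**PK measures (Description of laboratory assays, PK assay).** The exposure measure is defined as "The geometric mean area under the concentration-time curve through the sampling time of the last quantifiable" active-metabolite concentration, with Cmax and Tmax recorded alongside it. The section sets no time zero at the prasugrel dose and no common post-dose window.

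**Comparisons (Study endpoints, sample size calculation and statistical analysis).** Only group 2 versus group 1 on PRU at 4 hours is powered. Beyond that, "all other end points will be considered exploratory and will include the comparisons of PD and PK parameters", across all arms and time points. The same section applies ANCOVA to between-group comparisons at each time point, without multiplicity correction. It does not limit PK comparisons to groups 1 and 2.

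**Why PK matters here (Background).** An earlier trial is faulted because "there was no comparator arm in which prasugrel was either given alone or at the end of cangrelor infusion", and because PK assessments, "pivotal to help elucidate a DDI, were not performed".

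**The concern.** AUC to the last quantifiable sample compares arms fairly only if the arms are sampled over similar times since the dose. Here the same wall-clock schedule gives group 3 about half the post-dose follow-up, and nothing before 1 hour after its dose. A lower group 3 AUC would therefore be produced by the schedule, yet could be read as lower exposure with end-of-infusion dosing.

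The artefact could also mask a real difference between groups 2 and 3. If concomitant dosing truly reduced exposure in group 2, a group 3 AUC pushed down by its sampling could offset or reverse that difference. Group 3 is the stated standard-of-care strategy, so readers are likely to look at that contrast.

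**Working it through.** **1. Count the samples.** Seven time points are one baseline plus six later ones, which agrees with the plan. Re-expressed as time since prasugrel, for a 2-hour infusion:

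| Nominal sample | Groups 1 and 2 | Group 3 |
|---|---|---|
| 30 min | 0.5 h | before dose |
| End of PCI | variable | before or at dose |
| 1 h | 1 h | before dose |
| 2 h | 2 h | at dose |
| 3 h | 3 h | 1 h |
| 4 h | 4 h | 2 h |

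That is six post-dose samples against two. For longer infusions the last two samples move with the end of infusion, so group 3 still has 1 h and 2 h only.

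**2. One worked profile.** The documents give no half-life or Tmax, so these are assumptions: a one-compartment profile with Tmax 0.5 h, half-life 1 h, no lag, no assay limit and no separate end-of-PCI sample, identical in every arm. As fractions of the peak, the concentrations at 0, 0.5, 1, 2, 3 and 4 h are 0, 1, 0.819, 0.420, 0.210 and 0.105. By linear trapezoid:

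- Group 1: 0.5×(0+1)/2 + 0.5×(1+0.819)/2 + (0.819+0.420)/2 + (0.420+0.210)/2 + (0.210+0.105)/2 = 0.250 + 0.455 + 0.620 + 0.315 + 0.158 ≈ 1.797
- Group 3 (0, 1, 2 h): (0+0.819)/2 + (0.819+0.420)/2 = 0.410 + 0.620 ≈ 1.029
- Ratio: 1.029/1.797 = 0.57, with no difference in exposure

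Two parts make up the gap. Group 1's area to 2 h is 0.250 + 0.455 + 0.620 ≈ 1.324. The shorter window contributes 1.324/1.797 = 0.74 and the missing 0.5 h sample contributes 1.029/1.324 = 0.78; 0.74 × 0.78 ≈ 0.57. The Cmax ratio is 0.819/1 = 0.82. Group 3's Tmax can only be recorded as 1 h or 2 h after its dose.

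**3. Does re-indexing alone help?** On the randomization clock, group 3's values are 0 up to 2 h, 0.819 at 3 h and 0.420 at 4 h. The area is again 0.410 + 0.620 ≈ 1.029. Moving time zero changes Tmax but neither AUC nor Cmax, so the cause is the window and not the clock. (Recent P2Y12 antagonists are an exclusion, so a zero pre-dose level is reasonable.)

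**4. Range over assumptions.** The grid used Tmax 0.5-1 h; half-life 0.5-4 h; lag 0-1 h; assay limit none or 5% of peak; and end of PCI absent or at 0.35-2 h. This gives 4,200 scenarios, all with identical PK in every arm.

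| Group 3 / group 1 | Result |
|---|---|
| AUC[0-tlast], no lag, no limit | 0.44-0.65 |
| AUC[0-tlast], all scenarios, linear trapezoid | 0.20-0.98 |
| AUC[0-tlast], all scenarios, linear-up/log-down | 0.20-1.003 (7 of 4,200 at or above 1) |
| Cmax, all scenarios | 0.75-1.00 |

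The true AUC(0-2 h) is 0.53-0.89 of AUC(0-4 h) without lag and 0.30-0.58 with a 1 h lag, so the shorter window can only lower the figure. Sparse early sampling can act in either direction. Outside this grid, Tmax 0.25 h with half-life 0.5 h gives a Cmax ratio of 0.51.

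**5. Check of the remedy.** If AUC(0-2 h) is computed in every arm from 0, 1 and 2 h only, identical curves give 1.00 by construction. Truncating at 2 h but keeping the early samples in groups 1 and 2 leaves 0.70-0.89 without lag and 0.52-1.38 over lags up to 1 h. A common window is therefore not enough; the sample times must match.

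**The case against.** **The harmful comparison is partly inferred.** The plan speaks of comparisons at each time point, while AUC, Cmax and Tmax are not time-point measures and are said only to be calculated or recorded. This is fair, but they are the only PK parameters the plan names, and it compares PK parameters between all arms. The inclusive reading is the reasonable one. Comparing concentrations at the nominal 3 h and 4 h remains valid as a comparison of strategies; it is just not evidence about drug disposition.

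**The plan already keeps group 3 aligned.** The rule for long infusions does hold its samples at 1 h and 2 h after prasugrel. That credit stands, and it is what makes a matched analysis possible. It does not supply the missing early and late samples.

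**Group 1 already answers the interaction question.** The earlier trial lacked both comparators and either would have served; group 2 versus group 1 PK would still show a real fall in exposure. This stands and limits the importance of the point.

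**Stronger readings to avoid.**

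- A reader might infer that the primary result is biased. It is not biased by the group 3 delay, because groups 1 and 2 take prasugrel at the same time. The shift of group 2's late samples when its infusion exceeds 2 hours is a separate matter and adds no weight here.
- A reader might infer a known reversal between groups 2 and 3. If group 2's exposure were 30% below group 3's, the no-lag range would show group 3 lower by 7-37% (0.648/0.7 = 0.93; 0.443/0.7 = 0.63). The full range gives 0.196/0.7 = 0.28 to 1.003/0.7 = 1.43, so reversal is possible but not established.
- A reader might infer that group 3's dosing time is at fault. Nothing here bears on it; the problem and the remedy are analytic.

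**Conclusion.** The point holds for exploratory PK contrasts that involve group 3, and for nothing else. The two-versus-six sample count follows directly from the Study design text. The direction is well supported: group 3's AUC[0-tlast] is expected to be lower, and its Cmax lower or equal at nominal times, when true PK is identical. Expected is the right word, since a few lagged scenarios reach a ratio of 1.

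The size is not determined by the documents. It rests on assumed one-compartment profiles: about 0.44-0.65 without lag, about 0.2-1.0 with lag or an assay limit. No single percentage should be quoted as the bias.

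The plan should be changed, because exploratory status does not remove a systematic schedule effect and the correction is cheap. It is not a threat to the trial's main conclusion.

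**What to change.** Add to the PK assay description and the statistical section wording such as:

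*Full-profile AUC, Cmax and Tmax of the active metabolite will be compared for group 2 versus group 1 only. Group 3 will be compared with the other arms only on samples matched for time since prasugrel: concentrations at 1 h and 2 h, or AUC(0-2 h) computed in every arm from the nominal 0, 1 and 2 h post-dose samples only, using actual times. Otherwise group 3 PK will be descriptive.*

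The matched samples are the essential part.

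**Cost.** One paragraph, plus a PK dataset indexed to the prasugrel dose with actual dose and draw times. No new samples and no change to treatment.

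**Limitations to state.** No full-profile PK claim can be made for group 3. The three-point area is coarse: over the assumed profiles it is 0.46-1.22 of the true AUC(0-2 h). If absorption lag differs between arms by 0.25-0.5 h, it can differ by up to about 41% despite identical disposition. Blood is drawn from the arterial sheath until the end of PCI and from a vein afterwards (Blood sampling and Laboratory assessments). A matched 1 h sample may therefore be arterial in groups 1 and 2 but venous in group 3; recording the draw site would let this be examined.
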